5.3.2. Analysis of relapse-related variables

Full details of all relapses are presented in a listing for AP3 on the PAS.

5.3.2.1. ARR up to end of Analysis Period

ARR for confirmed relapses up to the end of the Analysis Period is analyzed for AP3 on the PAS according to the NB model described in Section 6.12.1.

The model includes the number of confirmed relapses in the Analysis Period for each subject as the response variable, treatment as a factor and the logarithm of time in the Analysis Period (years) as an offset variable.

Mean model-based estimates of the ARR by treatment, as well corresponding 95% CIs are derived. In addition, rate ratios together with corresponding 95% CIs are derived for the following comparisons:

- ponesimod 20 mg vs. Ponesimod 10 mg;
- ponesimod 40 mg vs. Ponesimod 10 mg;
- ponesimod 40 mg vs. Ponesimod 20 mg.

The analysis of ARR for confirmed relapses is summarized in a table by treatment:

• Number of confirmed relapses per subject: descriptive statistics;

CONFIDENTIAL – FOIA Exemptions Apply in U.S.

- Number of confirmed relapses per subject: frequency counts and percentages for categories 0, 1, 2, 3, 4, and 5+;
- Total number of confirmed relapses: sum;
- Total time in Analysis Period (subject years): sum;
- Raw ARR: total number of confirmed relapses/total time in Analysis Period;
- ARR estimate and 95% CI from a NB model, together with the dispersion parameter from the model;
- Rate ratios and 95% CIs for the comparisons listed.

ARR for all relapses is analyzed as described above for confirmed relapses

5.3.2.2. ARR in the Post-treatment-emergent Period

Summary statistics are presented for ARR in the post-treatment-emergent period, as defined in Section 5.3.1.4.

The following summary is presented for the Post-Treatment DMT subgroup (Any DMT, including ponesimod), No DMT)), where the Post-Treatment DMT subgroup is defined in Section 5.5.6 and the list of DMTs is provided in Table 11 in Section 6.5.1.

- Number of confirmed relapses per subject: descriptive statistics;
- Number of confirmed relapses per subject: frequency counts and percentages for categories 0, 1, 2, 3, 4, and 5+;
- Total number of confirmed relapses: sum;
- Total time in Analysis Period (subject years): sum;
- Raw ARR: total number of confirmed relapses/total time in Analysis Period;

This table is also presented for all relapses.

A listing of confirmed/all relapses in this period is also presented.

5.3.2.3. ARR by year

ARR by year for confirmed relapses is analyzed for AP3 on the PAS, as described for ARR up to the end of the analysis period in Section 5.3.2.1 above. A similar analysis for the number of unconfirmed and confirmed (all) relapses will be provided. Mean model-based estimates of the ARR by year and by treatment, as well corresponding 95% CIs are derived. A summary table and a bar chart are produced to present the ARR by year.

5.3.2.4. Sensitivity analyses of ARR

ARR up to last treatment in the Analysis Period +7

ARR for confirmed relapses up to last treatment in the Analysis Period + 7 days is analyzed separately for AP3 on the PAS, in the same way as described for ARR up to end of the Analysis Period in Section 5.3.2.1 above.

This sensitivity analysis was conducted for the Interim Analysis CSR and will not be conducted for the Final CSR.

ARR adjusted for additional baseline covariates

ARR for confirmed relapses up to end of the analysis period is analyzed for AP3 on the PAS using the same model as described in Section 5.3.2.1 above, adjusted by treatment, number of documented relapses (≤ 1 and ≥ 2) in the past 24 months prior to core¹ baseline, EDSS at ponesimod baseline (≤ 3.5 and > 3.5). A similar analysis for the number of unconfirmed and confirmed (all) relapses will be provided.

¹ Although the model considers relapses over the ponesimod period, the number of documented relapses in the past 24 months prior to extension baseline is not available, and so the value collected at the start of the core study is used as a proxy.

This sensitivity analysis was conducted for the Interim Analysis CSR and will not be conducted for the Final CSR.

5.3.2.5. Time to first confirmed/any relapse up end of the Analysis Period

Time to first confirmed relapse is analyzed for AP3 on the PAS, using the Kaplan-Meier method and Cox proportional hazards model, as described in Section 6.12.2.1 and 6.12.2.2.

The reference time is the study day, i.e., days elapsed since start of treatment with ponesimod.

The results of the Kaplan-Meier analysis are summarized in a table including:

- Number of subjects at risk, with an event and censored, KM estimates (unstratified) and corresponding CI, at intervals of 48 weeks;
- Median, 25th and 75th percentiles of the survival function together with corresponding CIs.

The hazard ratio and corresponding 95% CI based on a Cox proportional hazards model including treatment as a factor are presented in a separate table for the following comparisons:

- ponesimod 20 mg vs. Ponesimod 10 mg;
- ponesimod 40 mg vs. Ponesimod 10 mg;
- ponesimod 40 mg vs. Ponesimod 20 mg.

The results of Kaplan-Meier analysis are also presented graphically, including the KM estimates and corresponding CIs at the time points specified above up to the timepoint where at least 10% of subjects in each group are still at risk, as well as the hazard ratios and CIs from the Cox proportional hazards model.

Time to first 'any' relapse (all relapses) is analyzed as described above for confirmed relapses.

As a sensitivity analysis, time to first confirmed relapse is analyzed as described above, with a stratified log-rank test as described in Section 6.12.2.1 to include the additional baseline covariates: number of documented relapses (≤ 1 and ≥ 2) in the past 24 months prior to core baseline, EDSS at ponesimod baseline (≤ 3.5 and > 3.5). This sensitivity analysis was conducted for the Interim Analysis CSR and will not be conducted for the Final CSR.

5.3.2.6. Other relapse-related characteristics

Other relapse-related characteristics are summarized by treatment group separately for AP3 on the PAS. This includes the following:

- Number (%) of subjects with at least one: relapse, , relapse treated with corticosteroids; for all relapses up to end of the Analysis Period, confirmed relapses up to end of the Analysis Period.
- Number (%) of subjects without any (confirmed or total) relapse.
- Number (%) of relapses (out of total number of relapses) treated with corticosteroids and descriptive statistics for continuous data for relapse duration (days); for all relapses up to end of the Analysis Period as well as for confirmed relapses up to end of the Analysis Period.
- Number (%) of relapses classified as mild/moderate/severe; for all relapses up to end of the Analysis Period as well as for confirmed relapses up to end of the Analysis Period.
- Number of confirmed relapses, number of all relapses, ratio of confirmed vs. all relapses; for relapses up to end of the Analysis Period for all relapses up to end of the Analysis Period as well as for confirmed relapses up to end of the Analysis Period

As described in Section 5.3.1.5, relapses requiring hospitalization will not be included in the summaries.

A listing of all relapses including hospitalizations, administration of corticosteroids, severity of relapse will be presented.

5.3.3. MRI-related variables

MRI data are provided from a central reader (MIAC). The following parameters are evaluated by MIAC:

Name of MRI test	MRI test code	Unit of MRI test
Total number of T1 Gd+ lesions	T1Gd_R	
Total volume of T1 Gd+ lesions	T1Gd_Vol	mm ³
Number of new or enlarging T2 lesions (without gadolinium-enhancement)	T2New_R	
Total volume of T2 lesions	T2_Vol	mm ³
Percentage brain volume change since Visit 2 (AC-058B201)	PBVC_V2	%
Percentage brain volume change since Visit 11 (AC-058B201)	PBVC_V11	%

Table 7:MRI parameters

All available MRI data are considered valid.

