EDSS increase of 0.5 point or 1-point increase in 1 to 3 FS*	EDSS increase of 1 or 2 points or 2-point increase in 1 or 2 FS* or 1-point increase in 4 or more FS*	Exceeding moderate relapse criteria: EDSS increase of 2.5 points or 2-point increase in 3 FS* or 3-point increase in 1 FS* or 2-point increase in more than 2 FS*

Table 7:Severity of relapse

* excluding the bowel and bladder, and mental FS.

Note: The EDSS increase is the increase observed at the EDSS assessment associated with the relapse, as compared the preceding EDSS assessment (performed prior to the relapse).

3. Time to 24-week confirmed disability progression up to end of the study.

Disability progression is defined as an increase of at least one full point in the EDSS score (or 1.5 points if the baseline EDSS was 0, or 0.5 points if the baseline EDSS was equal or greater than 5.5) with or without relapse, confirmed at the next scheduled EDSS assessment at least 24 weeks later (or if missing, at the next available scheduled EDSS assessment). The time to event is defined as the time from initiation of study treatment until the first EDSS assessment meeting the criteria for disability progression.

- 4. Other relapse-related endpoints:
 - Annualized total relapse rate.
 - Time to first (total) relapse.
 - Number of (confirmed and total) relapses.
 - Number of patients without any (confirmed and total) relapse.
 - Number of patients with a relapse requiring corticosteroid treatment.
- 5. MRI-related endpoints:

Confidential

EudraCT 2009-011470-15 EDMS-ERI-206617631

- Number of Gd+ lesions per patient recorded on T₁-weighted MRI scans at all assessments.
- Number of patients with no Gd+ lesions on T₁-weighted MRI scans at all assessments.
- Total volume of Gd+ lesions per patient on T₁-weighted MRI scans at all assessments.
- Number of new or enlarging lesions per patient on T₂-weighted MRI scans at all assessments.
- Change from baseline to all assessments in total lesion volume per patient on T₂-weighted MRI scans.
- Number of combined unique active lesions (Gd+ lesions plus new or enlarging T₂ lesions without gadolinium-enhancement) per patient on MRI scans at all assessments.
- Percentage change of brain volume from Visit 2 (from AC-058B201) up to the end of the study.
- Percentage change of brain volume from Visit 11 (from AC-058B201) up to the end of the study.
- 6. Neurological endpoints:

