5.3.3.2. New or enlarging T2 lesions and T2 volume

For summaries of new or enlarging T2 lesions (T2New_R) over time, the number of lesions is assigned to the timepoint in which they fall, as defined in Table 9 below. As the number of new or enlarging lesions is always relative to the previous assessment, if the observation period for the scan crosses the boundary of a time window, the lesions are allotted **proportionally** to the time windows which they cross. For example, if a subject has a scan at Week 24, and the next scheduled scan occurs at Week 72, the Week 72 scan will count the number ("x") of new or enlarging T2 lesions since Week 24. In this case x/2 lesions would be allocated to the Week 0-48 window, and x/2 lesions would be allocated to the Week 48-96 window.

Time windows are derived from time since first administration of ponesimod according to the schedule defined in Table 9 below.

Time window displayed	Time window (weeks)
Week 0-48	0 - <48
Week 48-96	48 - <96
Week 96-144	96 - <144
Week 144-192	144 - <192
Week 192-240	192 - <240
Week 240-288	240 - <288
Week 288-336	288 - <336
Week 336-384	336 - <384
Week 384-432	384 - <432
Week 432-480	432 - <480
Week 480-528	480 - < 528
Week 528-576	528 - < 576
Week 576-624	576 - < 624
Week 624-672	624 - < 672
Week 672-720	672 - < 720

Table 9:	MRI time window	definition: scan	mapping for new o	r enlarging T2 lesions
----------	-----------------	------------------	-------------------	------------------------

The following variables are derived for T2 lesions per subject using the above time windows:

- Number of new or enlarging T2 lesions (T2New_R) per MRI time window (as derived in Table 9 above) in AP3;
- No new or enlarging T2 lesions during each MRI time window in AP3.

The following additional variables are derived for T2 lesions per subject: Only scheduled scans are considered, however premature EOT scans are included.

- Cumulative number of new or enlarging T2 lesions over Analysis Period (for AP3), derived as the sum of the number of new or enlarging T2 lesions at each scheduled scan during the Analysis Period;
- Absence of new or enlarging T2 lesions over the Analysis Period (for AP3), derived where the sum of the number of new or enlarging T2 lesions at each scheduled scan during the Analysis Period is zero;
- Time (years) from first administration of ponesimod to last MRI scan at which T2 was measured in the Analysis Period (for AP3). Only scheduled scans are used for this derivation.

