5.3.3.3. Combined unique active lesions (CUAL)

The following variables are derived per subject for CUAL:

- Total number of CUAL derived as the number of new or enlarging T2 lesions at each scheduled scan* within the Analysis Period, plus the number of T1 Gd + lesions at each corresponding scheduled scan within the Analysis Period where new or enlarging T2 lesions were measured (AP3), and corresponding number categorized (0, >0** 5, >5 10, >10 15, >15 20, >20 25, >25)
- Cumulative number of CUAL over the Analysis Period, derived as the sum of all new or enlarging T2 lesions at each scheduled scan* within the Analysis Period, plus the number of T1 Gd + lesions at each corresponding scheduled scan within the Analysis Period where new or enlarging T2 lesions were measured (AP3);
- Cumulative number of CUAL over the Analysis Period as derived above, categorized into the following categories: 0, 1-5, 6-10, 11-15, 16-20, 21-25, 26-30, 31-35, 36-40 and 41+ (AP3).

* Excluding T1 Gd+ lesions measured at the core scheduled visits at Week 4, 8, 16 and 20. This restriction is necessary to avoid double-counting lesions when the MRI scans are less than 12 weeks apart, as only total (new + persisting) T1 Gd+ lesions are collected, but the derivation of CUAL should consider only new T1 Gd+ lesions. As T1 Gd+ lesions are assumed not to enhance for more than 12 weeks, it is assumed that the number of T1 Gd+ lesions counted when the scans are at least 12 weeks apart is equivalent to the number of new T1 Gd+ lesions.

** Fractional values are possible and reflect allocation of T2 lesions proportionally to adjacent time-windows.

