5.3.4.2. New or enlarging T2 lesions

The cumulative number of new or enlarging T2 lesions (as defined in Section 5.3.3.2) is analyzed separately for AP3 on the PAS, as described in Section 5.3.4.1 for the cumulative total number of T1 Gd+ lesions. The logarithm of the time up to the last MRI scan at which T2 was measured in the Analysis Period (years) is used as an offset variable. This analysis was conducted for the Interim CSR and is not planned to be conducted for the Final CSR.

The number of new or enlarging T2 lesions per MRI time window (as defined in Section 5.3.3.2) is summarized descriptively by treatment group as described in Section 5.3.4.1 for the cumulative number of T1 Gd+ lesions, and is presented in both a table and a figure for AP3 on the PAS.

The total T2 lesion volume per MRI timepoint and corresponding change from ponesimod baseline in total T2 lesion volume per MRI timepoint are summarized descriptively in the same way.

The number of subjects with no new or enlarging T2 lesions (lesion-free) in the Analysis Period is summarized by treatment group separately for AP3 on the PAS: frequency counts and percentages. The denominator for percentages is the number of subjects with at least one MRI scan at which T2 was measured during the Analysis Period.

All T2 lesion and volume data are presented in a listing for AP3 on the PAS.

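### The SAP's only T2 count is labelled non-enhancing but serves as the protocol's unrestricted T2 endpoint and T2 lesion-free status; if the label is wrong, CUAL double-counts instead

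*SAP*

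**What the plan says.** Protocol 3.10.1 lists two separate MRI endpoints. One is "Number of new or enlarging lesions per patient on" T2-weighted scans, with no exclusion of enhancing lesions. The other is CUAL, which adds to the Gd+ lesions only those new or enlarging T2 "lesions without gadolinium-enhancement) per patient on MRI scans at all assessments". Protocol 5.3 and 5.4 also name the T2 count and CUAL separately.

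SAP 5.3.3, Table 7, gives one T2 count from the central reader, T2New_R: "Number of new or enlarging T2 lesions (without gadolinium-enhancement". SAP 5.3.3.2 then drops the qualifier: "For summaries of new or enlarging T2 lesions (T2New_R) over time" introduces the windowing rule, and "Number of new or enlarging T2 lesions (T2New_R) per MRI time window" is a derived variable. The cumulative count and the absence of T2 lesions are also described there without it. SAP 5.3.4.2 keeps two T2 count outputs for the Final CSR. One is a per-window table and figure. For the other, "The number of subjects with no new or enlarging T2 lesions (lesion-free) in the Analysis Period is summarized". The negative binomial model of cumulative T2 lesions is not repeated.

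SAP 5.3.3.3 derives CUAL as the T2 count "plus the number of T1 Gd + lesions at each corresponding scheduled scan within the Analysis Period" at which T2 was measured, with no overlap subtracted. The tables of changes and clarifications in SAP 6.2 do not mention a restriction of the T2 endpoint.

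**The concern.** The protocol wants every new or enlarging T2 lesion counted. The SAP variable, read as labelled, is the non-enhancing component of CUAL. A new lesion that is still enhancing at its first scan would be missing from the T2 summary. A subject whose new lesions were all enhancing when scanned would be reported as T2 lesion-free.

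At stake are the T2 lesion-free percentage and the per-window T2 figure over up to about twelve years of treatment. The omission also depends on scan spacing, and spacing changes over the study, so part of any trend across windows could come from the schedule. If the label is loose instead, the fault moves to CUAL, the MRI count that the Final CSR still models.

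**Working it through.** **1. One of the two rules is wrong.** At a given scan let N be the new or enlarging T2 lesions that do not enhance, E those that do, and G the Gd+ count.

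| | T2 endpoint | CUAL |
|---|---|---|
| Protocol 3.10.1 | N + E | G + N |
| SAP, if T2New_R = N (label right) | N: short by E | G + N: agrees |
| SAP, if T2New_R = N + E (label wrong) | N + E: agrees | G + N + E: over by E |

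Both SAP rules match the protocol only if E = 0.

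**2. Direction if the label is right.** N cannot exceed N + E, so counts are equal or too low. N + E = 0 implies N = 0 but not the reverse, so lesion-free is equal or too high. SAP 5.3.3.2 counts each scan against the previous one, so an omitted lesion is not new at the next scan. It enters later only if it enlarges.

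**3. Dependence on scan interval.** The documents state no figure to reproduce, so this is an illustration.

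- Scan intervals L: Protocol 3.11.1.1 schedules MRI at E7, E9 and E13 (Weeks 24, 48 and 96 of TP1), then yearly, which is 48 weeks in visit spacing. Protocol 3.12.3.1 places P1, which has an MRI, 12 weeks after the last TP1 visit.
- Enhancement duration d: the SAP gives only a ceiling, "As T1 Gd+ lesions are assumed not to enhance for more than 12 weeks". Values below 12 weeks are assumptions.
- Further assumptions: lesions arise at a constant rate, and every new lesion enhances for d weeks from onset.

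Share counted = 1 − min(d/L, 1):

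| d (weeks) | L = 12 | L = 24 | L = 48 |
|---|---|---|---|
| 2 | 0.833 | 0.917 | 0.958 |
| 4 | 0.667 | 0.833 | 0.917 |
| 8 | 0.333 | 0.667 | 0.833 |
| 12 | 0 | 0.50 | 0.75 |

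With a flat true rate, a 48-week interval shows 0.917/0.833 = 1.10 (d = 4) to 0.75/0.50 = 1.5 (d = 12) times the rate of a 24-week interval.

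**4. The later level is not uniform.** Take a subject on ponesimod since the core study. E7 falls at ponesimod Week 48 and E9 at Week 72. For the Weeks 48–96 window at d = 12:

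- P1 follows E9: (24 × 0.50 + 12 × 0 + 12 × 0.75)/48 = 21/48 = 44%.
- E13 is the next scan: (24 × 0.50 + 24 × 0.75)/48 = 30/48 = 63%.

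Neither reaches the 75% that applies to purely yearly scanning.

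**5. Lesion-free status.** With a Poisson mean of m true lesions per 48 weeks (assumed), the true lesion-free share is exp(−m) and the reported share is exp(−m × share counted). Ranges run from d = 4 to d = 12.

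| m | True | Reported, 24-week scans | Reported, one 48-week scan |
|---|---|---|---|
| 0.25 | 77.9% | 81.2–88.2% | 79.5–82.9% |
| 0.5 | 60.7% | 65.9–77.9% | 63.2–68.7% |
| 1 | 36.8% | 43.5–60.7% | 40.0–47.2% |
| 2 | 13.5% | 18.9–36.8% | 16.0–22.3% |

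**The case against.** The best defence is that little depends on this count. All objectives are exploratory, and the cumulative T2 model is not run for the Final CSR. CUAL, which replaces it, adds the enhancing lesions back. CUAL has a zero category over the whole analysis period with the same denominator as the T2 lesion-free output, and Gd+ lesion-free status is reported by timepoint. T2 lesion-free status is not itself a protocol endpoint. The restriction is visible in Table 7, SAP 5.3.3.2 cites the variable by code, and no output shells are available to show what the titles will say. All dose groups share one MRI schedule, so no distortion between doses is claimed.

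The defence can add that the counting rule rests on one parenthesis. The reading rules sit in an MRI manual outside these documents, and the worked example in SAP 5.3.3.2 mentions no enhancement restriction.

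Most of this stands, and it limits the consequence. It does not remove the mismatch. A correct CUAL table beside a mislabelled T2 table does not make the latter the protocol endpoint, and if the parenthesis is wrong the error falls on CUAL.

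**Conclusion.** The mismatch holds on the text alone: one T2 count cannot serve both the unrestricted T2 endpoint and a CUAL sum without overlap, unless no new or enlarging T2 lesion ever enhances. If the Table 7 label is right, the direction is fixed: counts equal or too low, lesion-free equal or too high. The shortfall tends to be larger at shorter intervals. The size cannot be derived from the documents. The illustrative shares (83% against 92%, or 50% against 75%) assume a constant rate and that every new lesion enhances.

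A reader might infer that the first 48 weeks show only 25–75% of true lesions, followed by a false rise of up to three-fold to a steady 75–92%. The documents do not support that. It treats the 12-week ceiling as every lesion's duration at the upper end, and it needs core T2 reads at Weeks 12 and 24, which are not stated. It also fails for Weeks 48–96, where the same model gives about 44–63% at 12 weeks. Nor is it established that the T2 counts are too low, because that depends on the label.

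This should be fixed. It concerns exploratory, descriptive outputs and is not critical.

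**What to change.** Confirm with the central reader whether T2New_R excludes enhancing lesions.

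- **If it does:** report the protocol T2 endpoint from a total new or enlarging T2 count, where the reader has one. Otherwise title every T2New_R output as new or enlarging non-enhancing T2 lesions, and base lesion-free status on T2New_R = 0 and Gd+ = 0 at the scans used. That flag is equivalent to the CUAL = 0 category already derived.
- **If it does not:** correct the Table 7 label and remove the overlap from CUAL in SAP 5.3.3.3.

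Record the outcome in SAP 6.2 in either case.

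If the label is right and no total count exists, the cost is one query to the reader, some retitling and one changed flag, using data already held. A total count would need supply from the reader, and removing overlap from CUAL would need the number of lesions counted in both components. The lesion-free percentage may become less favourable.
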